2. SELECTION CRITERIA

All of the study's inclusion and exclusion criteria must be met by Day 0 (first visit) for the subject to be eligible for the treatment phase of the study.

2.1. Inclusion Criteria

- 2.1.1** Subject is ≥ 18 years of age
- 2.1.2** Patient with a wound deemed suitable for treatment with RD1
- 2.1.3** Prior to inclusion of an ulcer in the study, each wound will be reviewed for eligibility by an independent assessor using a central online review process that includes images of the ulcer.
- 2.1.4** Ulcer free of clinical signs of infection. (Subjects with wound infection at the screening visit may be treated and re-screened for participation in the study after eradication of the infection).
- 2.1.5** Post-debridement, ulcer free of necrotic tissue.
- 2.1.6** For foot ulcers, Subject has adequate vascular perfusion of the affected limb, as defined by Ankle-Brachial Index (ABI) ≥ 0.65 and ≤ 1.2
- 2.1.7** HbA1c $\leq 12.0\%$ (diabetic patients)
- 2.1.8** Subject or legal authorized representative must be willing to comply with the protocol including having blood drawn to create the RD1.
- 2.1.9** Female subjects who are capable of conceiving must use an acceptable form of contraception in order to participate in the study (acceptable forms of contraception include condoms for males and contraceptive pills or IUDs for women).

2.2. Exclusion Criteria

- 2.1.10** Presence of active underlying osteomyelitis.
- 2.1.11** Patient with a proven sepsis established by a blood culture in the past 2 weeks, or confirmed active infection likely to interfere with trial, such as urine tract infection
- 2.1.12** Known malignancy in the reference wound bed or margins of the wound
- 2.1.13** Exposure of blood vessels or organs at the base of the reference wound
- 2.1.14** History of alcohol or substance abuse, within the previous 2 months
- 2.1.15** Subject has participated in another clinical trial involving a device or a systemically administered investigational study drug or treatment within 30 days of day 0 visit.
- 2.1.16** Subject is currently receiving (i.e., within the past 30 days) or scheduled to receive a medication or treatment which, in the opinion of the Investigator, is known to interfere with, or affect the rate and quality of, wound healing (e.g., systemic steroids (more than 10mg per day), immunosuppressive therapy, autoimmune disease therapy, cytostatic therapy within the past 12 months, , radiation therapy to the ulcer area, vascular surgery, angioplasty or thrombolysis).
- 2.1.17** Subject has been treated with wound dressings that include growth factors, engineered tissues or skin substitutes (e.g., Regranex®, Dermagraft®, Apligraf®, GraftJacket®, OASIS®, Primatrix®, Matristem®, etc.) within 30 days of randomization or is scheduled to receive during the study.
- 2.1.18** Subject has been treated with hyperbaric oxygen within 5 days of screening or is scheduled to receive during the study.
- 2.1.19** Wound on a patient who has a life expectancy of less than 6 months.
- 2.1.20** Cannot withdraw blood in the required amount technically.
- 2.1.21** Known coagulation problems, abnormal thrombocytes level or if heparin is given intravenously. Patients who are taking orally Coumadin, Aspirin, or Plavix (clopidogrel) will not be excluded.
- 2.1.22** Hemoglobin anemia (< 9 g/dL).
- 2.1.23** Subject has an infectious disease, such as Acquired Immune Deficiency Disease (AIDS) or HIV, Hepatitis C, Hepatitis B, Human T-lymphotropic virus or Syphilis
- 2.1.24** Women who are pregnant or currently breast feeding.

2.3. Investigator and Site Selection

2.3.1 Investigators

Study investigator, will be instrumental in choosing the principal and co-investigators for the trial.

2.3.2 Sites Selection

All of the sites will have had training in Good Clinical Practices (GCP) with National Institutes of Health certification in the ethical treatment of human subjects.

3. DIAGNOSTIC EVALUATIONS

3.1. Laboratory Tests

HbA1c
Complete blood count
Coagulation tests – PT and PTT

4. STOPPING RULES

4.1. Individuals

4.1.1 Infection

An infection that cannot be controlled or interferes with treatment in such a way that a treatment failure is likely to occur.

If cellulitis or local wound infection occurs, the Investigator may interrupt treatment in order to address this adverse event. The Investigator will treat cellulitis or local wound infection in accordance with his clinical judgment. Systemic antibiotic therapy is permitted; however, topical antimicrobials are not permitted in combination with RD1. Investigator may interrupt treatment in order to apply topical antimicrobials and resume treatment later (in the time frame of 16 weeks only)

4.1.2 Venipuncture

Inability to complete a successful venipuncture resulting in complete loss of venous access.

4.1.3 Ulcer Deterioration

Ulcer deterioration, determined by physician discretion.

4.1.4 Health Deterioration

Any health deterioration or acute situation requiring hospitalization or likely to interfere with treatment and resulting in treatment failure.

4.1.5 Necrotic tissue:

Appearance of substantial necrotic tissue.

4.3. Study

4.2.1 $\geq 25\%$ of ulcers have deteriorated (Ulcer deterioration is determined by physician discretion)

4.2.2 $\geq 50\%$ of ulcers have been infected.

4.2.3 ≥ 25% of patients have dropped out because of problems with venipuncture.

5. LONG TERM FOLLOW-UP

5.1. General

Following the 16-week study the subjects will be treated according to standard wound care. Subjects are kept in a database allowing follow-up studies to be conducted. Additional studies would only be performed with Ethics Committee approval and patient consent.

6. MISSED VISITS

If a subject misses a visit, the site is to make every effort to have the subject return as soon as possible to make-up the visit. Once the subject is seen, he/she is to return to his/her original visit schedule.

Patients who miss more than 2 two consecutive visits during the treatment phase will be withdrawn.

7. ADVERSE EVENTS

The NCI CTCAEv4 scale will be used to grade adverse events/serious adverse events.

7.1. Serious Adverse Events

Serious Adverse events (SAE) are defined as any adverse change in the subject's medical condition that meets any of the following criteria: results in death; is life-threatening; requires inpatient hospitalization or prolongation of existing hospitalization; results in persistent or significant disability/incapacity (grades 3-5 using NCI CTCAEv4 scale).

Any serious adverse event that occurs during the subject's participation in the study, even though it may not be considered related to the study device by the Principal Investigator, must be reported on the case report forms. If an SAE is thought to be related to the device, it must also be catalogued under device-related adverse events.

SAEs are reported to the Institutional Review Board (IRB)/Ethics committee and the sponsor within 24 hours of recognition by the Principal Investigator.

Subjects who develop serious adverse effects should be followed until the event or effect resolves or stabilizes.

SAEs will be determined at each visit or whenever the site investigator is notified of an AE and determines it to be an SAE, and then recorded. The following information regarding SAEs will be collected:

- Description of the event
- Onset date
- Time of onset
- End date
- End Time
- Relationship to study device (e.g., yes, no, likely, unlikely)
- Action taken
- Outcome.

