7.2. Device-related Adverse Events

Device-related Adverse Effects (DRAEs) are previously recognized or unrecognized adverse events directly related to the use of the RD1. These DRAEs will be reported to the IRB/EC and sponsor within 24 hours of the initial discovery of the event. They are also captured in the case report forms. A DRAE that is also determined to be an SAE will also be reported separately under SAE protocol.

Subjects who develop DRAEs should be followed until the event or effect resolves or stabilizes.

All DRAEs will be collected at each visit and recorded. The following information regarding AEs will be collected:

- Description of the event
- Onset date
- Time of onset
- End date
- End time
- Severity
- Categorization of event in relation to study device (Possible, Probable, Definite; Unrelated/Unlikely categories should be moved to the SAE/AE list).
- SAE (Y/N)
- Action taken
- Outcome.

Examples of incidents that might be DRAEs include, but are not limited to:

- Complications related to venipuncture but not including lack of venous access
- Infections appearing within 2-4 days of device application.
- Bleeding at the wound site that is not related to any debridement
- Any allergic reactions
- High pain related to product application or removal

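### The SAE definition in section 7.1 carries a severity range, and its causality terms and record fields do not match those for DRAEs and AEs, so SAE and DRAE rates depend on how a site reads the text

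*Protocol*

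**What the plan says.** Section 7 sets the grading rule: "The NCI CTCAEv4 scale will be used to grade adverse events/serious adverse events".

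Section 7.1 defines an SAE by four alternative criteria (death, threat to life, hospital admission or a longer stay, lasting disability), any one of which suffices. The fourth carries the bracket: "results in persistent or significant disability/incapacity (grades 3-5 using NCI CTCAEv4 scale". The SAE record has eight fields: description, onset date and time, end date and time, relationship, action and outcome. Relationship is given as "Relationship to study device (e.g., yes, no, likely, unlikely". SAEs go to the IRB and the sponsor within 24 hours.

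Section 7.2 defines DRAEs as "adverse events directly related to the use of the RD1", and has a record field for "Categorization of event in relation to study device (Possible, Probable, Definite; Unrelated/Unlikely categories should be moved to the SAE/AE list". DRAEs are also reported within 24 hours, and the record has a serious yes/no item.

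Two rules link the lists. From section 7.1: "If an SAE is thought to be related to the device, it must also be catalogued under device-related adverse events". From section 7.2: "A DRAE that is also determined to be an SAE will also be reported separately under SAE protocol".

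Section 7.3 gives the AE record, which lists severity but neither relationship nor seriousness. Sections 1.1 and 13.2.2 make the rates of SAEs, AEs and DRAEs a secondary safety objective and endpoint.

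**The concern.** Seriousness (what the event led to), severity (its grade) and causality (its relation to the device) are separate attributes. Sections 7.1 to 7.3 mix them and record them unevenly.

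The bracket puts a grade range inside an outcome definition without saying what it qualifies. Events that are severe but meet none of the four outcomes can then fall on either side of the line.

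For causality, the SAE and DRAE records use different terms. An investigator with a possibly related SAE finds no such term among the SAE examples, and is not told which SAE terms send the event to the DRAE list.

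Two things are at stake. The SAE and DRAE rates may differ between the two nursing facilities (section 1.3) for reasons of reading alone. The reading of the bracket also decides whether some events get 24-hour reporting.

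**Working it through.** The protocol states no SAE or DRAE rate, so there is no figure to reproduce. The check is a comparison of definitions and fields, plus one line of arithmetic.

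**1. What the bracket can mean.** There are two workable readings:

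- Reading A: it qualifies disability only.
- Reading B: it makes any grade 3-5 event serious.

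| Event | Reading A | Reading B |
|---|---|---|
| Grade 2, admitted to hospital | SAE | SAE |
| Grade 3, meets none of the four outcomes, judged unrelated | AE, no 24-hour report | SAE, 24-hour report |
| Grade 3, meets none of the four outcomes, on the DRAE list | DRAE, 24-hour report | DRAE and SAE, 24-hour report |

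The readings differ for grade 3-5 events that meet no outcome criterion. Reporting time differs only where such an event is not also a DRAE, because DRAEs have the same 24-hour rule. This does not depend on what each grade means, which the protocol does not define.

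**2. What the records can hold.**

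| Item | SAE record (7.1) | DRAE record (7.2) | AE record (7.3) |
|---|---|---|---|
| Severity or grade | not listed | listed | listed |
| Relationship to device | four example terms | three terms kept, two moved off | not listed |
| Serious yes/no | not listed | listed | not listed |
| Seriousness criterion met | not listed | not listed | not listed |
| Action and outcome | listed | listed | listed |

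Section 7 requires SAEs to be graded, so the gap is in the SAE field list and not in the intention.

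**3. Whether the causality terms line up.** Section 7.1 offers yes, no, likely and unlikely. Section 7.2 uses Possible, Probable and Definite, and moves Unrelated and Unlikely elsewhere. Unlikely is the only shared term. Plausible matches are no with Unrelated, likely with Probable and yes with Definite, but the protocol states none of them, and Possible has no match.

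The copying rule in section 7.1 depends on whether the SAE is thought related, with no cut-off on its own terms. Section 7.2 keeps Possible events on a list that it defines by direct relation. An event moved to the AE list as Unrelated or Unlikely arrives where no relationship field is listed to hold that judgement.

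**4. Size per subject.** The shift in a subject-level rate from one reclassified subject is 1/N. Section 13.1 sets 60 completers, and section 1.3 gives up to 120 or more enrolled.

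- N = 60: 1/60 = 1.7 percentage points.
- N = 120: 1/120 = 0.8 percentage points.

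The number reclassified is not derivable. If it were 1 to 6 subjects (an assumption), the shift would be 1.7 to 10.0 points at 60 (6/60) and 0.8 to 5.0 points at 120 (6/120). A subject counts as reclassified only if no other event already places that subject in the category.

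**The case against.** The strongest reply is that this is loose drafting with safeguards around it, and much of that stands.

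- A reader might infer that an SAE needs both an outcome criterion and grade 3-5, so that a grade 2 admission is lost. The text does not support this: the criteria are alternatives, and admission suffices alone.
- A reader might infer that the SAE terms exclude a possible relation. They are introduced only as examples, so a site could write Possible.
- Section 7.2 already names five causality levels and, by moving Unrelated and Unlikely off the list, implies that Possible or higher stays.
- Cross-listing runs both ways, and the DRAE record flags seriousness.
- A reader might infer that SAEs go ungraded or that the data could never be sorted out. Section 7 requires grading, the CRF is not shown, and description, action and outcome allow partial reconstruction.
- Sites are trained and monitored on safety reporting (section 11.3), and the study stopping rules in section 4 do not use SAE or DRAE counts.

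These points limit the consequences but do not settle what the bracket qualifies. Training and monitoring can only enforce the definition as written. The cross-listing rules work only after the event has been judged serious or related, and those are the judgements left open. The cut-off implied in section 7.2 is not carried into section 7.1 and sits awkwardly with that section's own definition by direct relation.

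**Conclusion.** The point holds as a fault in definitions and data fields. A grade 3-5 event that meets none of the four outcomes can be an SAE at one facility and not at the other. A possibly related SAE has no listed causality term and no stated route to the DRAE list. The SAE record lists neither the grade nor the criterion needed to check the classification.

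The size is 1.7 points per reclassified subject at 60, or 0.8 points at 120. The total is unknown because the protocol gives no event rates, and divergence between sites is an inference from the wording. The causality gap affects the DRAE count and not the reporting time of an SAE, which is due within 24 hours anyway.

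Severity is minor to moderate: a secondary safety endpoint and expedited reporting are affected, and the primary endpoint is not.

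**What to change.** - In section 7.1, delete the bracketed grade range, so that seriousness rests on the listed outcomes.
- Add CTCAE grade and seriousness criterion met to the SAE record.
- Use the section 7.2 causality terms (Unrelated, Unlikely, Possible, Probable, Definite) in sections 7.1 and 7.3, which gives the AE record a relationship field.
- State once that Possible or higher is a DRAE. Let this replace the direct-relation wording in section 7.2 and the wording in section 7.1 about an SAE being thought related.

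The cost is small edits to sections 7.1 to 7.3 and to the CRF. Severe but non-serious events (grade 3 or higher) would need their own table. Clearer definitions may also change which events fall under 24-hour reporting, so sites should be told when the change takes effect.

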7.2. Device-related Adverse Events

Device-related Adverse Effects (DRAEs) are previously recognized or unrecognized adverse events directly related to the use of the RD1. These DRAEs will be reported to the IRB/EC and sponsor within 24 hours of the initial discovery of the event. They are also captured in the case report forms. A DRAE that is also determined to be an SAE will also be reported separately under SAE protocol.

Subjects who develop DRAEs should be followed until the event or effect resolves or stabilizes.

All DRAEs will be collected at each visit and recorded. The following information regarding AEs will be collected:

- Description of the event
- Onset date
- Time of onset
- End date
- End time
- Severity
- Categorization of event in relation to study device (Possible, Probable, Definite; Unrelated/Unlikely categories should be moved to the SAE/AE list).
- SAE (Y/N)
- Action taken
- Outcome.

Examples of incidents that might be DRAEs include, but are not limited to:

- Complications related to venipuncture but not including lack of venous access
- Infections appearing within 2-4 days of device application.
- Bleeding at the wound site that is not related to any debridement
- Any allergic reactions
- High pain related to product application or removal

7.3. Adverse Events

An adverse event (AE) is defined as any adverse change in the subject's medical condition including any deterioration, or exacerbation of a pre-existing medical condition that is observed by the Investigator or reported by the subject.

All AEs will be collected at each visit and recorded. The following information regarding AEs will be collected:

- Description of the event
- Onset date
- Time of onset
- End date
- End time
- Severity
- Action taken
- Outcome.

Examples of anticipated AEs include, but are not limited to:

- Infection not related to device application
- Increase in stage of wound
- Sudden increase in ulcer area or depth
- Peripheral edema or localized swelling
- New ulcer
- Systemic fever

7.4. Subject Referral to another Facility

In case a patient is referred to another facility during the course of the study treatment, due to an adverse event, **RD1 must be removed prior to subject referral and study treatment should be stopped**. In some cases, with sponsor approval, study treatment could be resumed following subject's return to the SNF.

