9. LOST TO FOLLOW-UP

Subjects who are lost to follow-up will be included in the primary safety analysis but only patients who complete the study will be included in the secondary objectives analysis; where wound area data are missing, imputation using LOCF (last observation carried forward) will be used.

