13. DATA ANALYSIS

13.1. Study Population and Sample size

- 13.1.1 The safety population will be all subjects who receive at least one RD1 treatment.
- 13.1.2 The intent-to-treat population (ITT) will be all subjects who complete the study.
- 13.1.3 Sample size is initially set as 60 but enrollment will be increased if necessary to compensate for drop-outs so that 60 patients complete the trial.

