13.2.1. Primary Endpoint

Efficacy- The performance of RD1 in terms of wound progress towards closure in wounds deemed suitable for treatment with RD1 (ITT population)

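### Sections 4.1.4, 6 and 7.4 can give different outcomes for the same referred subject, and with a completers-only efficacy set the sponsor's case-by-case approval can influence who is analysed

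*Protocol*

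**What the plan says.** Protocol section 7.4 covers a subject referred to another facility because of an adverse event. Its default is that "RD1 must be removed prior to subject referral and study treatment should be stopped". Its exception is: "In some cases, with sponsor approval, study treatment could be resumed following subject's return to the SNF". It names no criteria and does not refer to the other rules.

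Two other sections can apply to the same subject:

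- Section 4.1.4, under the stopping rules for individuals: "Any health deterioration or acute situation requiring hospitalization or likely to interfere with treatment and resulting in treatment failure". It does not mention resumption either way.
- Section 6: "Patients who miss more than 2 two consecutive visits during the treatment phase will be withdrawn". It makes no exception for time spent in another facility.

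For comparison, section 4.1.1 lets the investigator interrupt treatment for an infection and "resume treatment later (in the time frame of 16 weeks only". Sections 1.4 and 1.5 cap total treatment at 16 weeks for every subject.

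On the analysis side, section 13.1.2 states: "The intent-to-treat population (ITT) will be all subjects who complete the study". Section 13.2.1 assigns the primary endpoint to that set, and 13.2.2 does the same for the efficacy secondary endpoints. Section 9 says that "only patients who complete the study will be included in the secondary objectives analysis", with last observation carried forward for missing wound areas. Sections 1.2 and 13.1.3 increase enrolment until 60 subjects complete.

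**The concern.** A rule on interrupting treatment is normally a matter of conduct. Here it also decides who is analysed. A subject who resumes and reaches the end of the study is in the efficacy set. A subject who is withdrawn is out of it and is replaced. There is no control arm in which the same selection would occur and partly cancel.

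The selection could be related to outcome. Referral under 7.4 follows an adverse event, and section 7.3 includes worsening of the wound itself among the anticipated adverse events. No blinding is described, and section 11.1 gives sponsor representatives access to all study records and case report forms. Approval can therefore be given or withheld when the course of the wound is known. Two sites could also handle identical subjects differently and both claim compliance.

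**Working it through.** **1. The rules side by side.** Take a subject hospitalised for an adverse event during the treatment phase.

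| Section | Consequence | Route back | Criteria |
|---|---|---|---|
| 4.1.4 | individual stopping rule | not mentioned | none beyond the trigger |
| 7.4 | treatment stopped | possible, if the sponsor approves | none |
| 6 | withdrawal once three or more consecutive visits are missed | not mentioned | visit count only |

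**2. When section 6 applies.** Visits are every 7 days, plus or minus 3 (1.4, 1.6.3.1). More than 2 consecutive misses means at least 3, for example those due on days 7, 14 and 21.

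- Counting nominal dates, the absence spans 21 − 7 = 14 days, about 2 weeks.
- Counting a visit as missed only when its whole window has passed, the absence runs from day 4 to day 24, about 3 weeks.

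A shorter absence leaves 4.1.4 and 7.4 to be reconciled. A longer one brings in mandatory withdrawal under section 6, while 7.4 still speaks of resumption without saying that it yields.

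**3. The 16-week limit.** The cap in 1.4 and 1.5 covers resumed subjects too. What is open is whether time in another facility counts toward it. Section 4.1.1 settles this for infection; 7.4 does not.

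**4. Who counts as a completer.** Withdrawn subjects are not completers, since 1.2 replaces them. Completion is not otherwise defined. A subject stopped under 4.1.4 who attends the early termination visit (1.6.3.4) could be classed either way.

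**5. Size.** The protocol states no referral rate, closure rate or dropout rate, so there is no figure to reproduce. All rates below are assumed.

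*(a) Leaving out and replacing m referred subjects whose wounds do not close.* With h closures among 60 completers, the reported rate is h/60 and the all-treated rate is h/(60 + m).

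| h | h/60 | m = 3 | m = 6 | m = 12 | m = 15 |
|---|---|---|---|---|---|
| 30 | 50.0% | 47.6% | 45.5% | 41.7% | 40.0% |
| 42 | 70.0% | 66.7% | 63.6% | 58.3% | 56.0% |

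The overstatement is 2.4 to 10.0 points for h = 30 and 3.3 to 14.0 points for h = 42. This is the effect of a completers-only set, not of sponsor discretion as such.

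*(b) Selective resumption.* Take 60 treated, 12 referred, and 50% closure in the other 48 (24 closures).

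- If 4 of the 12 would close and only those 4 resume: (24 + 4)/(48 + 4) = 53.8%. With all 60 counted: 28/60 = 46.7%.
- If closure is 33% in the better 6 and 7% in the worse 6, and only the better 6 resume: (24 + 2)/54 = 48.1%. With all 60 counted: (24 + 2.4)/60 = 44.0%.
- If all 12 are stopped and dropped: 24/48 = 50.0%.

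Selective approval gives a rate above the strict stop in the first case and below it in the second. Even the sign of that comparison depends on the assumptions. In both cases, dropping subjects gives a higher rate than counting all of them.

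**The case against.** The best defence is that the rules can be read together. Section 7.4 has the same default as 4.1.4 and adds a specific exception. The closing words of 4.1.4 about treatment failure may qualify its hospitalisation trigger. Section 6 is mandatory and 7.4 only permissive, so resumption might be open only to subjects not already withdrawn. These readings are possible, but the text states none of them, and sites need to know which applies.

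A reader might go further than the documents allow in four ways:

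- *That 4.1.4 forbids return.* It is silent on the point.
- *That 7.4 allows resumption without time limit.* The 16-week cap in 1.4 and 1.5 applies; only the counting of time away is unclear.
- *That the sponsor decides who completes, and does so on wound progress.* Approval is a necessary condition, in effect a veto. The subject must also return and be willing, and the investigator must treat. Nothing says that wound progress informs the approval.
- *That the bias remains whichever analysis set is used.* Most of it runs through the completers-only set. With all treated subjects counted, a smaller problem remains: a subject not resumed has an early termination measurement and then carried-forward values, while a resumed subject has later measurements.

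**Conclusion.** The point holds as a matter of reconciliation with a consequence for the analysis. Sections 4.1.4, 6 and 7.4 can lead to different outcomes for the same referred subject, with no stated precedence and no criteria for approval. Because efficacy is analysed in completers and withdrawn subjects are replaced, that open choice can influence who is in the efficacy set.

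The size cannot be estimated from the protocol. The illustrations show that a handful of dropped subjects can move a closure rate by a few points or more, but every rate in them is assumed. They do not measure the effect of sponsor approval, and a reader should not take a spread of several points as an estimate of bias. The absence of blinding is inferred from the single-arm design and the sponsor's access to records. The safety population, defined by at least one treatment, is unaffected.

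**What to change.** Reconcile 4.1.4, 6 and 7.4 into one rule for hospitalisation or referral, fixed in advance, with its clinical content left to the sponsor's clinicians. It should state:

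- which section takes precedence;
- how time in another facility counts toward the missed-visit rule and the 16-week limit of 1.4 and 1.5;
- whether such a subject counts as having completed the study.

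Record each resumption decision and its reason on the case report form.

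Whatever the decision, keep the subject in the efficacy denominator, with 13.1.2 and section 9 amended to match, and measure and photograph the wound at week 16 if the subject is back in the nursing facility. The resumption decision then cannot change who is counted.

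The cost is a wording amendment, an entry on the case report form, and one extra photograph and measurement for a few subjects off treatment. The reported closure rate may be slightly less favourable.
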